During the randomized vitamin E treatment phase, patients will be continue to be seen by the nutritionist every 8 weeks for individual follow-up visits and to reinforce components covered during the initial 12 week lifestyle intervention. During the extended treatment phase, the patients will be seen by the nutritionist every 12 weeks. Patients will complete the 3-day food intake diary and IPAQ every 24 weeks during the randomized treatment and extended treatment phases. The data obtained from these diaries and questionnaires will be used to ensure that differences in outcomes observed between the different vitamin E groups are not due to differences in adherence to lifestyle changes. Although part of the effect of treatment may be due to lifestyle intervention, it should affect all treatment groups in a similar manner and the effect of vitamin E will be deduced from the dose response.

Detailed in-patient assessment

At the beginning of the randomized-dose treatment phase, patients will be admitted to the Clinical center for a detailed histological, physiological and biochemical analysis, including:

- 1. History and physical examination: including vital signs, weight and anthropomorphic measurements.
- 2. Fasting blood tests: chem-20, GGT, CBC, PT, PTT, serum insulin, c-peptide, lipid panel, apolipoproteins, total free fatty acids, hemoglobin A1c, alpha-fetoprotein, ferritin, iron, transferrin saturation, immunoglobulins, TSH, C-reactive protein, PSA and vitamin E levels
- 3. Research blood: 10 ml of serum will be separated from collected blood and stored in 2 separate aliquots in -80°C for determining serum levels of hormones, cytokines and adipokines, injury markers (such as CK-18 fragments), and for archival storage. 10 ml of plasma will be separated from collected blood and stored at -80°C for analysis of oxidative stress measures.
- 4. NKT and NK cell analysis: 40 ml of blood will be drawn for analysis of NKT and NK cell phenotype and effector function. Additional 8 ml of serum tube (8 ml) will be used to provide autologous serum for in vitro functional assays. The frequency of performing these assays is detailed in table 1.
- 5. Urine tests: urinalysis, pregnancy test (for women of child-bearing potential) and 24-hour urine collection for creatinine clearance and protein and uric acid

excretion. A 5 ml urine sample will be stored at -80°C for oxidative stress measurements.

6. Imaging:

- a. Magnetic resonance imaging (MRI):

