 - i. MR spectroscopy to quantitatively measure liver fat content.
 - ii. Liver volume estimation
 - iii. Adipose tissue distribution: measurement of total abdominal adipose tissue, visceral adipose tissue and subcutaneous adipose tissue volumes.
- b. Total body mass, total body fat mass and bone mineral density will be determined using dual energy x-ray absorptiometry (DEXA).

7. Insulin sensitivity:

- a. Insulin-modified frequently sampled intravenous glucose tolerance test (FSIVGTT)¹⁹ after a 12-14 hour fast, intravenous access will be achieved in both arms. After 15 minutes of comfortable rest, blood samples will be drawn at, 10 and 1 minute before glucose injection. At time 0, 300mg/kg of glucose, in the form of dextrose 50% in water, will be injected over 1-2 minutes. Blood samples will be drawn at 0, 1, 2, 3, 4, 5, 6, 7, 8, 10, 12, 14, 16 and 20 minutes. At 20 minutes, IV insulin will be given at a dose of 4 mU/min*kg for 5 minutes. Blood sampling will continue at 22, 23, 24, 25, 26, 27, 28, 30, 40, 50, 60, 70, 80, 100, 120, 150 and 180 minutes. All samples will be analyzed for plasma glucose, insulin and free fatty acid concentrations²⁰. Glucose effectiveness and insulin sensitivity will be calculated according to the minimal model using the MINMOD software.
- b. Hepatic insulin sensitivity will be estimated using the HOMA-IR2 model.
- c. Adipose tissue insulin sensitivity will be estimated at the basal state by the HOMA-FFA model.
- 8. Liver biopsy: a percutaneous liver biopsy will be performed under local anesthesia, with the patient in a fasting state. Tissue will be used for histological evaluation, RNA analysis, immunological studies, measurement of oxidative stress and archival storage.
- 9. Subcutaneous adipose tissue biopsy: subcutaneous adipose tissue will be removed from the abdominal region by needle aspiration under local anesthesia. The sample will be submitted for histological evaluation, RNA analysis and an additional fraction will be used to for ex vivo studies (see below).
- 10. Resting energy expenditure (REE) measurement will be performed at the patient bedside.
- 11. Studies under other protocols. Participation in the following protocols will be offered to all patients in the study if eligible. Refusal to enroll in these additional studies will not preclude patients from participating in this protocol.

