Randomization will be done by the Clinical Center pharmacy Protocol Support Service and will be stratified by the result of the liver biopsy (classified as definite steatohepatitis, steatosis without steatohepatitis, or borderline^{21, 22}) and by the presence or absence of diabetes mellitus type 2 at enrollment. Patients will be monitored on weeks 1, 2, 3, 4, 8, 12, 16, and 20 of treatment. On each visit, fasting blood tests for Chem-20, insulin, C-peptide, free fatty acids and vitamin E levels will be drawn, vital signs including weight will be measured and a symptom questionnaire will be administered. CBC, lipid panel, apolipoproteins and urinalysis will be drawn every 4 weeks. A nurse will determine weight, vital signs and symptoms on every visit. A physician will evaluate the patients every 4 weeks. A serum sample for research purposes will be drawn on each visit and stored in -80°C.

On week 4 of treatment, patients will be admitted for a second liver biopsy and adipose tissue biopsy, and will have a repeat of the MR spectroscopy and FSIVGTT.

On week 24 of treatment, all patients will be admitted for an exit work-up, identical to the detailed in-patient assessment described above, but without the biopsies.

During the treatment, patients will be recording medication intake on a diary that will be collected every visit and will be used to assess compliance.

Extended Treatment Phase

On discharge, all patients will be offered to continue treatment with open-label vitamin E 800 IU/d (two 400 IU capsules taken once daily) for up to 120 more weeks, after which, an exit liver biopsy will be performed. Enrollment into the extended treatment phase is optional and refusal will not exclude the patient from the study. The medication intake diary will be used in this phase as well.

After 24 weeks in the extended phase (week 48 of the study), patients will undergo an additional MR spectroscopy. Based on the results of the MRS and liver enzymes, the response will be assessed prior to deciding on treatment continuation. For this purpose, response is defined as a decline of >=25% in ALT or normal ALT or normal AST or an absolute decline of more than 2% in liver fat content by MRS. The response criteria are selected to be sensitive, but not necessarily specific, aiming to predominantly identify patients who are not responding to treatment and in which continuation is futile. Based on the response assessment there are three possible outcomes (Figure 4):

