⁵ NK/NKT cell analyses – On Run-in phase, first admission and week 144 will be drawn for all patients. On weeks 4 and 24 these will be performed only on the 200 IU/d and 800 IU/d arms (total volume 48 ml). On week 144 only 30 ml will be obtained. Will not be performed if Hb < 10 g/dL.

⁶ FSIVGTT – total blood volume drawn 120-150 ml. Will not be performed if Hb < 10 g/dL.

⁷ Possible lowering of vitamin E dose based on week 48 results (see Figure 4).

Analysis of the study

End points

Primary end points

There are two primary clinical end points in the study. The primary biochemical response is defined in a binary manner as an end-of-treatment AST <=32 or ALT <=35 U/L. The selection of these cut-off values is based on a pilot analysis by us that examined in an unbiased manner several rules for biochemical response and found this to be the one most strongly associated with histological response to treatment, irrespective of treatment modality³¹. We will also analyze the absolute change in ALT and AST from pre-treatment to end-of treatment as continuous parameters of the effect of treatment on liver enzymes. Patients who at the time of starting vitamin E treatment have normal liver enzymes will be excluded from this analysis. The primary physiological response is the absolute change in liver fat content as determined by comparing the ¹H-MRS results from pre-treatment to end of treatment.

Secondary end points

Secondary end points include: absolute and percent decrease in liver enzymes, decrease in GGT levels, percent reduction in liver fat.

A secondary analysis will analyze the effect of the lifestyle modification by comparing the end points between enrollment and the end of the lifestyle modification phase. Another analysis will determine the effect of increasing the dose of vitamin E by comparing the end points between the end of the randomized phase (week 24) to weeks 24 and 144 of the extended phase.

The kinetics of response will be determined by analyzing sequential ALT and AST measurements. Current data suggest biphasic response pattern to vitamin E and mathematical modeling will be applied to the results and will be compared between doses. Similar modeling will be applied to changes in liver fat content by ¹H-MRS.

Basic scientific end points

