Gene expression in liver and adipose tissue will be analyzed using microarray and quantitative PCR (qPCR) of tissue samples. Treatment-induced changes or comparisons between groups of patient (i.e. comparison of baseline expression between responders and non-responders) will be expressed as fold-induction.

NK and NKT cell changes in the serum and liver tissue will be analyzed using phenotyping and functional assays.

Oxidative stress will be measured in the serum, urine, liver and adipose tissue using TBARS assay, F₂-isoprostanes, 9-HODE, 13-HODE, SOD activity or similar measures. In women of child-bearing age, the phase of the menstrual cycle will be recorded on extended visits, as F₂-isoprostane levels can be affected by it.

Statistical analyses

Parameters of response to treatment will be analyzed by matched-pair comparison between pre-treatment and end of treatment values. Student's t-test will be used for values that are distributed normally while Wilcoxon's sign-ranked test will be used for non-parametric values. Categorical comparisons will be performed using X^2 or Fisher's exact test, as appropriate. The Cochran-Armitage test for trend will be used to test for a dose effect on the primary clinical end points.

To determine the effect of genetic variants, genotype-based analyses will be preferred to allelic analyses, with an additive model used primarily, unless other (dominant or recessive) models seem more appropriate. Linear or ordinal logistic regression will be used.

All analyses will be done with and without stratification for the presence of diabetes mellitus.

An $\alpha \le 0.05$ will be used to determine statistical significance.

Sample size calculation

The main goal of the study is to understand and characterize the mechanism of response to vitamin E. An important goal of the study is to simultaneously collect liver and adipose tissue to determine the site of action of the vitamin E and the relative contribution of each tissue to the disease. For most of the planned end points, including changes in liver fat content by ¹H-MRS and the basic scientific end points, there is not enough pre-existing data to allow for accurate sample size calculation.

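### The primary liver-fat end point has no between-dose model, and no planned analysis uses the pre-treatment liver fat already measured as a covariate

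*Combined protocol and SAP*

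**What the plan says.** Primary end points opens: "There are two primary clinical end points in the study". One is a binary biochemical response. The other is continuous: "The primary physiological response is the absolute change in liver fat content", from pre-treatment to end of treatment. Percent reduction in liver fat is listed only under Secondary end points.

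Statistical analyses gives two rules that bear on the continuous end point:

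- "Parameters of response to treatment will be analyzed by matched-pair comparison between pre-treatment and end of treatment values", by t-test or Wilcoxon test.
- "The Cochran-Armitage test for trend will be used to test for a dose effect on the primary clinical end points".

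It adds: "All analyses will be done with and without stratification for the presence of diabetes mellitus". The regression mentioned in that section belongs to the genetic-variant analysis.

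The pre-treatment value is available. Detailed in-patient assessment includes "MR spectroscopy to quantitatively measure liver fat content", and Table 1 places this scan at the week-12 admission, before randomization, and again at week 24. Randomization (Vitamin E Treatment) is stratified by biopsy class "and by the presence or absence of diabetes mellitus type 2 at enrollment". Neither the strata nor the analysis uses the amount of liver fat.

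**The concern.** The paired tests ask whether fat changed within patients. They do not compare doses. Cochran-Armitage compares doses but needs a binary outcome. Whoever analyses the trial must therefore choose a between-dose method for liver fat after the fact, including whether to adjust for starting fat.

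That choice matters for this measure. The fat fraction is lipid over water plus lipid (Magnetic Resonance Spectroscopy), so a patient who starts at 6% cannot lose 10 points, while one who starts at 30% can. The inclusion criteria set no minimum fat fraction, and patients with steatosis only are treated alongside those with NASH. A wide spread of starting values is likely. Stratifying by biopsy class does not balance it, because steatohepatitis status is not a measure of fat quantity.

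Subtracting the baseline does not remove the dependence. A change score forces the slope of post-treatment on pre-treatment fat to equal 1. If loss grows with starting fat, the true slope is below 1 and change stays correlated with baseline. With about 25 patients per arm, the spread in starting fat then widens the interval for the dose effect, and chance imbalance between arms moves the estimate.

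**Working it through.** **The plan's own figure.** The only stated power, 80%, is for the biochemical end point: 25 per group and response rates of 10%, 20% and 45% (Sample size calculation). For a two-sided 5% Cochran-Armitage test with equal scores, the normal approximation gives 82.8% without and 78.1% with continuity correction. The exact conditional test gives 79.7%. Dose scores with continuity correction give 81.0%. So 80% is reproducible. The recruitment target also follows: 25/(1 − 1/6) = 30 per group, 90 in all. None of this concerns liver fat, which the same section says could not be sized for lack of data.

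**Inputs for liver fat.** From the documents: 25 evaluable per arm and alpha 5%. Sidedness is not stated; two-sided is taken. Not given, so assumed over ranges: SDs, pre/post correlation and effect size.

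**Formula.** Let r be the pre/post correlation, s0 the pre-treatment SD, and k the ratio of post- to pre-treatment SD.

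- Variance of raw change: s0²(1 + k² − 2rk).
- Residual variance after baseline adjustment: s0²k²(1 − r²).
- Difference: s0²(1 − rk)². This is never negative, and is zero when the slope rk equals 1.
- Ratio R of adjusted to raw variance: k²(1 − r²)/(1 + k² − 2rk), which is (1 + r)/2 when k = 1.

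Take an effect for which raw change has 80% power. Adjusted power is Φ(2.802/√R − 1.960), with 2.802 = 1.960 + 0.842.

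| r (k = 1) | R | Adjusted power | Equivalent n per arm (25 × R) |
|---|---|---|---|
| 0.5 | 0.75 | 90% | 18.8 |
| 0.6 | 0.80 | 88% | 20.0 |
| 0.7 | 0.85 | 86% | 21.2 |
| 0.8 | 0.90 | 84% | 22.5 |
| 0.9 | 0.95 | 82% | 23.8 |

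If the post-treatment SD shrinks to k = 0.8, R is 0.571, 0.628 and 0.608 at r = 0.5, 0.7 and 0.9, and power is 96%, 94% and 95%. With k = 1.1 and r = 0.9 the slope is 0.99, R is 1.00 and there is no gain.

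**Simulation of proportional loss.** Assumed: 25 per arm, lognormal baseline with mean 15% and CV 0.6, mean relative losses of 10%, 20% and 35% by dose, and a linear dose slope.

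| SD of relative loss | Power, raw change | Power, adjusted |
|---|---|---|
| 0.2 | 89% | 95% |
| 0.3 | 64% | 69% |
| 0.4 | 43% | 45% |

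With CV 0.4 the gain was 1 to 3 points. Other inputs (median 16%, log-SD 0.5, losses 5/12/25% or 10/20/35%, SD of loss 0.15 to 0.35) gave variance ratios of 0.74 to 0.94 and gains of about 1 to 6 points. Type I error was near 5% with or without adjustment.

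**Cost in degrees of freedom.** With 75 evaluable patients, an intercept and a dose slope leave 75 − 2 = 73. Baseline fat uses 1, three biopsy classes use 2 and diabetes uses 1, which leaves 73 − 4 = 69.

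**The case against.** Five points can be made for the plan.

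1. **The sized dose comparison is elsewhere.** Sample size calculation assigns the comparison of doses under primary aim 1 to the biochemical end point. This stands. A reader might infer from "the effect of vitamin E will be deduced from the dose response" (Run-in phase and lifestyle intervention) that the liver-fat comparison carries the main inference. The documents do not support that: the sentence concerns lifestyle effects shared across arms and does not mention MR spectroscopy. Still, the dose-effect test is planned for the primary clinical end points in the plural, and liver fat is one of the two.

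2. **There is no planned unadjusted model to criticise.** A reader might infer that the plan commits to an unadjusted between-dose comparison and so discards power. It does not; it names no valid between-dose method for a continuous change. The missing model is the more basic gap, and the covariate is part of filling it.

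3. **The gain may be small.** A rise from 80% to 90% needs r = 0.5 with equal SDs. In a rerun of the proportional-loss simulation the implied correlation was 0.70 to 0.86 at CV 0.6 and 0.58 to 0.78 at CV 0.4. This stands, so the upper end should not be quoted alone.

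4. **Percent reduction already relates loss to baseline.** In that rerun, percent change had more power than the adjusted analysis in all six settings. Power for raw, adjusted and percent change was 65/71/80% at CV 0.6 and loss SD 0.3, and 73/75/80% at CV 0.4 and loss SD 0.3. This stands in part. The simulated loss is proportional by construction, and percent reduction is only secondary, so it supports the primary analysis without adjusting it.

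5. **No bias is shown.** Correct. Randomization makes a raw-change comparison unbiased, and its type I error is near 5%. In a phase IIa study whose stated main goal is mechanism, this is a matter of efficiency.

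**Conclusion.** The point holds as a modest improvement to the second primary end point. The plan intends a dose test on liver fat, names no method that can deliver it, and leaves unused a covariate that is scheduled before randomization.

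The gains shown above, from nil to 10 power points with larger values only if the post-treatment SD shrinks, all rest on assumed SDs and correlations. Apart from the degrees of freedom spent, baseline adjustment does not lose precision against raw change. It also corrects the estimate for chance imbalance in starting fat. The power stated for the biochemical end point is not affected.

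**What to change.** In Statistical analyses, add that the dose effect on liver fat will be analysed by linear regression of the week-24 fat fraction (or its change) on dose. The covariates are the fat fraction from the week-12 admission scan and the randomization strata (biopsy class and diabetes). State the dose coding in advance. Report the adjusted dose slope and adjusted arm means with 95% confidence intervals.

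Confine Cochran-Armitage to the binary biochemical end point. Keep the paired tests as within-arm description and percent reduction as a supporting secondary end point.

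The cost is a few sentences of analysis text and four degrees of freedom. No additional scans, visits or patients are needed, and naming the model now removes a choice that would otherwise be made after the data are seen.

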We propose a phase IIa study to determine the optimal dose of vitamin E and its mechanism and site of action. In this study we aim to enroll up to 90 patients with NAFLD. Initially, all patients will undergo 12 weeks of intensive lifestyle modification. Following that, all patients will be randomized to treatment with 3 different doses of natural vitamin E (rrr- α -tocopherol at 200, 400 or 800 IU/d) for 24 weeks. The primary end points for efficacy are normalization of liver enzymes and reduction in liver fat contents by magnetic resonance spectroscopy. Patients will undergo liver and adipose tissue biopsies before vitamin E treatment and after 4 weeks of therapy, and the biopsy samples will be used to measure changes in gene expression and markers of oxidative stress. This will be coupled with extensive phenotyping before and after treatment using serological, radiological and dynamic endocrine testing and is aimed at finding the dose-response characteristics of vitamin E in NAFLD, and allowing us to understand the mechanism of its action.

After 24 weeks of randomized treatment, all patients will be switched to a dose of 800 IU/ml and will continue treatment for up to 30 months, at the end of which another liver biopsy will be performed. From this phase we will assess the effects of dose increase of vitamin E on liver enzymes and fat content, and will determine the effect of long-term treatment on histological outcome.

Table of Contents

Précis	3
Table of Contents	4
Introduction	6
Non-alcoholic fatty liver disease	6
Vitamin E	7
Vitamin E for NAFLD	8
Aims	10
Primary Aims:	10
Secondary aims:	10
Study design and methods	11
Overall design (Figure 3)	11
Initial screening and enrollment	12
Run-in phase and lifestyle intervention	12
Detailed in-patient assessment	14
Vitamin E Treatment	15
Extended Treatment Phase	16
Details of procedures	18
Adipose Tissue Biopsy	18
Liver Biopsy	18
Magnetic Resonance Spectroscopy	19
Justification for study design	19
Run-in phase	19
Liver biopsies	20
Absence of a control arm	21
Duration of treatment	21
Inclusion and exclusion criteria	21
Inclusion	21
Exclusion criteria	
Monitoring subjects and criteria for withdrawal of subject from the study	
Analysis of the study	
End points	27

Vitamin E for Non-Alcoholic Fatty Liver

Primary end points	27
Secondary end points	27
Basic scientific end points	27
Statistical analyses	28
Sample size calculation	28
Human subject protections	28
Rationale for subject selection	28

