There is no clear accepted duration of treatment for NASH and similar to other metabolic conditions like diabetes or hypertension, treatment is probably required for life. The kinetics of biochemical response in the previous vitamin E trials (figure 2) show near-plateauing at week 24, and suggest little incremental benefit will be achieved by extending treatment beyond that.

Inclusion and exclusion criteria

Inclusion

- 1. Clinical suspicion of NAFLD, defined by the presence of at least two of the following criteria:
 - a. Suggestion of liver fat by an imaging study (ultrasound, CT scan, MRI or MR spectroscopy) performed in the 6 months prior to enrollment.
 - b. Elevated aminotransferase levels (ALT > 31 U/L for men or > 19 U/L for women, or AST > 30 U/L) on at least two occasions in the 6 months preceding enrollment.
 - c. Presence of the metabolic syndrome, defined according to the modified AHA/NCEP criteria³⁰ as the presence of at least three of:
 - i. Abdominal obesity, defined as waist circumference > 102 cm for men or > 88 cm for women
 - ii. Elevated triglycerides (> 150 mg/dL) or the use of medication to lower triglycerides
 - iii. Reduced HDL cholesterol (< 40 mg/DL for men or < 50 mg/dL for women)
 - iv. Elevated blood pressure (> 135/80 mmHg) or use of medication for hypertension
 - v. Elevated fasting glucose levels (> 100 mg/dL) or use of anti-diabetic medication

For the purpose of inclusion, the presence of overt diabetes mellitus type 2 will be considered equivalent to the presence of the metabolic syndrome, even if the other criteria are absent.

- 2. Estimated average alcohol consumption < 30 g/d for men or < 20 g/d for women in the 6 months prior to enrollment and no binge-drinking behavior.
- 3. Age > 18 years at enrollment
- 4. Willingness to participate in the study

Exclusion criteria

- 1. Chronic infection with hepatitis C virus (HCV) or hepatitis B virus (HBV). Patients who were treated successfully for HCV and achieved sustained virological response can be eligible for enrollment > 18 months after treatment cessation. Patients who are inactive carriers of HBV (HBV DNA < 1000 copies/mL, HBeAg negative, Anti HDV negative) for at least 12 months prior to enrollment are also eligible. Patients receiving antiviral therapy are ineligible.
- 2. Concomitant liver disease such as autoimmune hepatitis, primary biliary cirrhosis, primary sclerosing cholangitis, Wilson's disease, alpha-1 antitrypsin deficiency.

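### The dose-increase analysis names no arm and no concurrent comparator group, although the continuing 800 IU/d arm could serve as one up to study week 48

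*Combined protocol and SAP*

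**What the plan says.** The Précis gives the extension phase a purpose: "From this phase we will assess the effects of dose increase of vitamin E on liver enzymes and fat content". Secondary end points carries this out in one sentence. It will "determine the effect of increasing the dose of vitamin E by comparing the end points between the end of the randomized phase", which is study week 24, and two later time points. The wording for those later points is "to weeks 24 and 144 of the extended phase". No arm, comparator group or test is named there. Statistical analyses gives a general method: "Parameters of response to treatment will be analyzed by matched-pair comparison between pre-treatment and end of treatment values". The same Secondary end points section does plan a between-dose comparison for the response kinetics, where "mathematical modeling will be applied to the results and will be compared between doses", but nothing similar for the dose increase.

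Three other parts bear on the point.

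- **Extended Treatment Phase:** every patient is offered open-label 800 IU/d, and entry is optional. At study week 48, non-responders stop treatment (and are withdrawn, according to the monitoring section). Patients from the 200 and 400 IU/d arms who responded, but gained nothing after the switch, return to their original dose.
- **Table 1:** routine and extended laboratory tests and MR spectroscopy (MRS) are scheduled at study weeks 24 and 48, whatever the original arm.
- **Secondary aims, item 1:** asks whether patients who did not respond to a low dose gain from a higher one.

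**The concern.** A before-after difference measures the dose effect plus whatever else changed. Other things do change at week 24: nutritionist visits go from every 8 to every 12 weeks, and clinic visits from every 4 to every 12. The Introduction also reports that, in the cited pediatric trial, improvement in the placebo group largely removed the ALT difference by two years.

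The protocol states the remedy itself when it discusses lifestyle effects: "it should affect all treatment groups in a similar manner and the effect of vitamin E will be deduced from the dose response". The dose-increase analysis, as worded, does not use that between-dose logic.

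What is at stake is the stated purpose of the extension and secondary aim 1. The population of that aim, low-dose non-responders, is not carried into any analysis in Secondary end points or Statistical analyses. The randomized dose comparison at week 24 is not touched.

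**Working it through.** **The plan's own figure.** No sample size or power is given for this analysis. The only stated power is 80% for the Cochran-Armitage trend test with 25 per arm and response rates of 10%, 20% and 45%. Exact enumeration (two-sided, equally spaced scores, continuity corrected) gives 79.7%, so it is reproduced. It does not bear on this point.

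**Inputs.** 30 patients per arm are recruited and 25 per arm are needed for analysis (Sample size calculation). So 60 or 50 patients step up, and 30 or 25 stay on 800 IU/d, if all continue. Effects and drifts are assumed, in SDs of the week 24 to 48 change, with equal SD in all arms. Tests are two-sided at 5%. The paired test is inferred from the general method.

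**What each comparison estimates.** Let c be the change common to all arms and d the effect of the dose increase.

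- 200 and 400 IU/d arms, before-after: c + d
- All three arms pooled, before-after: c + (2/3)d
- 800 IU/d arm, before-after: c
- 200 and 400 IU/d arms minus 800 IU/d arm: d

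**Paired test with d = 0** (noncentral t, n − 1 degrees of freedom, noncentrality drift × √n; for example 0.2 × √50 = 1.41):

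| Shared drift (SD) | n = 50 | n = 60 |
|---|---|---|
| 0 | 5.0% | 5.0% |
| 0.1 | 10.7% | 11.9% |
| 0.2 | 28.4% | 33.2% |
| 0.3 | 54.8% | 62.8% |

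**Hidden benefit.** A true effect of 0.40 SD with a shared worsening of 0.2 SD leaves 0.40 − 0.20 = 0.20 SD. Power at n = 50 falls from 79% to 28%.

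**Pooling, if it were done.** For d = 0.40 SD and no drift, 20,000 simulated trials give 61% power with 75 pooled patients against 79% with 50 low-dose patients, and 69% with 90 against 86% with 60.

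**Contrast with the 800 IU/d arm.** The standard error ratio to the paired analysis is √(1/60 + 1/30) / √(1/60) = 0.2236 / 0.1291 = 1.73; it is the same for 50 v 25.

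| | 60 v 30 | 50 v 25 |
|---|---|---|
| Detectable at 80% power, contrast | 0.63 SD | 0.70 SD |
| Detectable at 80% power, paired | 0.37 SD | 0.40 SD |
| Power for 0.40 SD, contrast | 42% | 36% |
| Power for 0.40 SD, paired | 86% | 79% |
| False positives if only the low-dose arms drift 0.2 SD | 14% | 13% |
| Same, drift 0.3 SD | 26% | 23% |

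If 60% enter the extension (assumed; 36 v 18), power for 0.40 SD is about 27%. For the primary biochemical end point the plan says "Patients who at the time of starting vitamin E treatment have normal liver enzymes will be excluded from this analysis". If that exclusion is carried over to ALT here and removes 20% to 40% of patients (assumed), the detectable difference becomes 0.71 to 0.82 SD (from 60 v 30) or 0.78 to 0.91 SD (from 50 v 25). Among week-24 non-responders at the plan's response rates, 27 + 24 = 51 v 16.5 gives 0.805 SD, and 22.5 + 20 = 42.5 v 13.75 gives 0.885 SD.

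**Week 144.** The week-48 rule was simulated with no effect of the dose increase.

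- *True levels fixed after week 24, visit errors independent:* over all patients not stopped, the false change is within 0.2% in ALT and 0.01 fat points.
- *Lasting individual changes with mean zero between weeks 24 and 48 (assumed SD 0.1 to 0.2 on log ALT, 0.5 to 1.5 fat points):* the rule keeps those who improved, and the false fall among patients not stopped is roughly 1% to 6% in ALT and 0.03 to 0.4 fat points.
- *Low-dose patients still on 800 IU/d:* even with fixed levels, a simulation with median ALT 70, within-patient variation of 15% to 35% and MRS error SD 1.5 gave false falls of 3% to 9% in ALT and 0.3 to 0.6 fat points. It left out the normal-AST route to response; including it would count more patients as improved and so reduce these figures.

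**The clock.** The extension starts at study week 24 and lasts up to 120 weeks, and 24 + 120 = 144. So 144 is a study week, while 24 in the same phrase is an extension week (study week 48).

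**The case against.** The strongest objection is power. Moving from the paired change to the contrast cuts power for a 0.40 SD effect from 79–86% to 36–42%, and optional entry cuts it further. This stands, and it is why the within-arm change should stay beside the contrast and not be replaced by it. But the paired test's extra power is for dose effect plus drift, not for dose effect alone.

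Second, equal drift across arms is doubtful. The plan expects 10%, 20% and 45% response, so the arms should reach week 24 at different levels, with different room to change. This also stands: the contrast removes only change that is equal across arms.

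Third, the protocol gives a reason to expect little drift. Earlier trials "show near-plateauing at week 24, and suggest little incremental benefit will be achieved by extending treatment beyond that". A reader might infer that the planned comparison has been shown to be biased; the documents do not support that. Nor do they exclude drift, because those trials gave vitamin E at 800 IU/d, and their plateau concerned biochemical response. It says nothing of the lower doses or of liver fat.

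Fourth, an analysis of a dose increase would naturally be read as covering patients whose dose increased, and secondary aim 1 and the week-48 rule point the same way. A reader might infer that the plan pools the 800 IU/d arm. It neither says so nor excludes it, so the dilution figures are conditional.

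Finally, food diaries and activity questionnaires are collected every 24 weeks in the extension and can help in judging lifestyle differences. They are not a named part of this analysis.

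**Conclusion.** The concern holds as a weakness of a secondary analysis that should be corrected. The plan attributes change after week 24 to the dose increase without naming the arms or using the concurrent randomized group that its own schedule provides. It would be too strong to say that there is no comparator at all, since week 24 is a within-patient reference; what is missing is a comparator group.

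The size depends on assumptions. A shared drift of 0.2 SD would raise false positives from 5% to 28% (n = 50) or 33% (n = 60); the documents give no estimate of drift.

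The week-144 comparison mixes doses and is selected on week-48 values. A reader might take comfort that selection bias over all patients not stopped is near zero, but that needs true levels to stay fixed after week 24, which the documents do not establish. With lasting individual changes the bias is a modest false improvement, and it is larger in those still on 800 IU/d.

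The mixed week labels are a small matter: Table 1 and Extended Treatment Phase identify the intended visits.

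**What to change.** In Secondary end points and Statistical analyses:

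1. Name the 200-to-800 and 400-to-800 arms as the dose-increase population.
2. Report their within-arm change from week 24 to study week 48 in MRS fat and ALT and, next to it, the difference from the concurrent change in the 800-to-800 arm, adjusted for the randomization strata (biopsy class, diabetes). Label both, and base any statement that attributes the change to dose on the contrast. State whether the normal-enzyme exclusion applies to ALT here.
3. Report low-dose week-24 non-responders as an exploratory subset for secondary aim 1, because they are defined after randomization. Report entry to the extension by arm.
4. Treat week 144 as descriptive, with dose received and retention shown.
5. Use one clock: study weeks 24, 48 and 144.

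The cost is analysis wording only; no visit or scan is added. The price in precision is a standard error 1.73 times the paired one. The write-up should state three limits: the contrast removes only change equal across arms; optional entry may differ by arm; and it does not show what low-dose patients would have done had they stayed on the low dose.
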